Recently we showed in PIVOT trial that patients after pneumatic retinopexy has less vertical distortion than patients after PPV. To the best of our knowledge, no study so far looked into retinal displacement after Pneumatic Retinopexy. Moreover, wide field FAF was not used in previous studies. We think there is a reason to believe that Pneumatic Retinopexy will cause less retinal displacement than PPV. Thus, we propose a prospective cohort study which will compare retinal displacement of patients after RD repair by PPV versus Pneumatic Retinopexy.

In addition, we wish to include VitreoRetinal Surgery, PA in Minnesota and Bhagwan Mahavir VitreoRetinal Services, Sankara Nethralaya in India as the site to study retinal displacement following RD repair using either SB or PPV with SB, since this practice has a much higher volume of those surgical methods.

II. Aim (SB and PPV+SB arm)

To compare retinal displacement and visual distortion of primary retinal detachment repair following scleral buckling (SB) versus scleral buckle combined with pars plana vitrectomy (PPV+SB).

III. Study design

(i) Hypothesis The primary study hypothesis is that scleral buckling alone may cause less retinal displacement and less visual distortion at the first 12 months for patients with primary retinal detachment than other methods.

(ii) Experimental design A prospective, cohort trial, evaluating scleral buckling alone and scleral buckling combined with vitrectomy outcomes for patients with primary retinal detachment.

(iii) Participants Patients presenting to vitreo-retinal service with rhegmatogenous retinal detachment. Eligibility for study participation will be ascertained by the examining physician at the time of presentation:

Inclusion criteria:

- Age \geq 18
- Diagnosis of macula off primary rhegmatogenous retinal detachment

Exclusion criteria:

- Previous retinal detachment and/or retinal detachment repair surgery in the study eye
- Retinal detachment with macula on.
- Patients with other retinal pathologies causing structural changes to the retina in the study eye, such as diabetic retinopathy, previous vascular occlusion (artery or vein occlusion), macular dystrophy, among others.
- Previous vitreoretinal surgery in the study eye
- Inability to come for follow ups up to 12 months.
- Inability to take FAF imaging due to neck stiffness or other medical issue.
- Inability to maintain post operation head positioning
- Mental incapacity

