- Inability to sign on informed consent.
- Patient is unwilling or unable to follow or comply with all study related procedures or to sign informed consent form

Criteria for participant withdrawal from study: - Patient withdraws consent

(v) Interventions

The only interventions in the study are performed at the 3 and 12 month postoperative visit, and include fundus imaging (FAF and OCT), and sensory testing with the M chart and the Aniseikonia test, as detailed below.

Participants will be chosen from those undergoing either scleral buckling alone or scleral buckling combined with vitrectomy for repair of a macula-off retinal detachment. Patients are not randomized to the procedure, rather the procedure is chosen by the surgeon in the best interests of the patient.

In the event of primary intervention failure (i.e. failure of retinal re-attachment following primary intervention), the decision to proceed with secondary intervention, and the nature of such intervention, will rest with the treating physician in conjunction with the patient. Secondary intervention may involve any surgical procedure, as deemed clinically appropriate.

Note: Additional laser retinopexy, cryotherapy, gas injection or head positioning are not considered a failure.

(vi) Timing of observationsSee flow diagram (Appendix 1)

Imaging

Fundus AutoFluorescence (FAF)

Fundus autofluorescence (FAF) imaging is a noninvasive imaging method and requires relatively little time. It highlights the fluorophores accumulating in lipofuscin (LF) within retinal pigment epithelium cells (RPE). No radiation is involved therefore this imaging method is safe without any clear contraindications.

M Chart

Recently, several tools have been developed for quantification of metamorphopsia severity including M-CHARTS (Inami Co., Tokyo, Japan). In the patients with metamorphopsia, a straight line appeared curved or irregular. On M-CHARTS, straight lines are replaced with dotted lines, and the dot intervals (range: 0.2° - 2.0°) are changed from fine to coarse. With increasing dot interval, the line distortion decreases until the dotted line becomes straight. The visual angle that denoted the dot interval of the line seen as straight was considered as the patient's M-CHARTS score. When a

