The following clinical data will be obtained from each patient: age, gender, extent of the detachment (quadrants), duration of subjective symptoms (days), vitreous status (presence/absence of vitreous hemorrhage), macular status (attached/on or detached/off), the location of main retinal tears (fundus sketch), refractive power (emmetropic, hyperopic, myopic <6 or > 6 diopters, lens status (phakic or pseudophakic) and medications in use.

(x) Sample size

Sample sizes were calculated to appropriately power the study. A total sample size of 40 subjects with macula-off detachments undergoing scleral buckles will be recruited. A second group of 40 subjects with macula-off retinal detachments undergoing combined vitrectomy and scleral buckle placement will also be recruited. Anticipating a dropout rate of 20%, we calculated a total of 100 patients in the entire study.

IV. Data management

Initial data collection (clinical examination findings, visual acuity, and questionnaire data) will take place in a paper format. Subsequently, this data will be transferred to a digital database (Microsoft Excel). Paper data will be stored in a locked filing cabinet in the principal investigator's office and away from the study data, and will be destroyed once digital data entry has taken place. The digital spreadsheet will be held on a password protected computer in a locked room, and an encrypted memory stick.^[1] At recruitment, each patient's name and date of birth will be obtained to facilitate onward administration of follow-up appointments and safety monitoring and stored on a face sheet (master linking log). The face sheets will be stored in a locked filing cabinet, away from the study data. Each patient will be allocated a unique study identification number, which will be used to label all paper and digital data pertaining to that patient. The face sheets (master linking log) and all paper/electronic data will be destroyed once publication takes place. The de-identified study data will be destroyed five years after publication has taken place.

V. Consent:

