Written, informed consent for imaging and sensory testing as part of the study will be obtained from each participant. Important: the clinical care of the patient will not be affected by the patient's participation or non-participation in this study of post-surgery imaging and sensory testing. Given that 12-month followup can be problematic for patients who live a great distance from the study sites, a 20% dropout rate is anticipated. There is no charge to the patient for the sensory testing, which is the only element that differs from standard care.

On no occasion should consent be obtained by the treating physician or study investigator.^[17] During working hours: The study will be introduced to the patient by the examining physician. Interested patients are directed to Research Technician who will obtain informed consent.

Late evenings / weekends: Informed consent may instead be obtained by the vitreoretinal surgery fellow (assuming that they are not the treating physician and will not be involved in the patient's surgery). The resident/fellow will be familiar with both interventions (SB and PPV+SB), the nature of the study and trained to the consent discussion and obtaining written informed consent. As retinal detachments are usually unilateral conditions, patients can still read the informed consent. If the patient has any bilateral visual impairment, a witness, usually being the accompanying relative of the patient or a staff member not involved in the study, will also be present.

VI. Data Analysis:

Continuous data: Data will be checked for normality.^[18] Normal data will be compared using a non-paired t-test. Non-normal data will be compared using non parametric tests. Categorical data: Chi squared test. Coefficients with 95% confidence intervals will be reported. A p-value of 0.05 will be considered for statistical significance. Data will be analyzed using SPSS (SPSS Inc., Chicago, IL). Per protocol analysis will be used.

VII. Safety Monitoring Plan

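### The primary comparison pools a US and an Indian site in a plain chi-squared test; if the procedure mix differs by site, a site difference in print detection would bias it.

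*Protocol*

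**What the plan says.** The last paragraph of Protocol section I brings in two practices in different countries for this sub-study: "we wish to include VitreoRetinal Surgery, PA in Minnesota", together with "Sankara Nethralaya in India as the site to study retinal displacement following RD repair using either SB or PPV with SB". No share of patients, and no share of either procedure, is given for either practice.

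Section III(v) describes the allocation: "Patients are not randomized to the procedure, rather the procedure is chosen by the surgeon in the best interests of the patient".

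Section III(x) sets the group sizes overall: "A total sample size of 40 subjects with macula-off detachments undergoing scleral buckles will be recruited". The PPV+SB group is likewise given a single overall figure of 40. Section III(viii) continues recruitment until the overall number is reached. Neither section refers to site.

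The primary outcome in III(vii) is binary: whether vessel prints are present on FAF. For such data section VI states "Categorical data: Chi squared test". It names no stratification, matching or model term for site. The list of clinical data under III(ix) covers patient and eye characteristics and includes neither site nor surgeon.

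**The concern.** The primary outcome is a yes/no reading of an image. How often prints are called present may differ between two practices for reasons unrelated to the operation, such as imaging equipment and field, reading habits, surgeons and posturing practice. Section I treats the field of view as a point of novelty ("wide field FAF was not used in previous studies"), but the FAF text in III(vi) fixes no device or field.

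A site difference does no harm to the comparison when both sites contribute the two procedures in the same proportion. With surgeon's choice and overall totals only, nothing in the plan ensures this. If the proportions differ, an unstratified test attributes part of the site difference to the procedure. Adjusting for the items listed under III(ix) would not reliably remove it, because site is not among them. At stake are the false-positive rate and the estimated difference on the primary outcome.

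**Working it through.** **The plan's own figure.** 40 + 40 = 80 evaluable patients, and 80 / (1 − 0.20) = 100, which matches the stated total. The 40 per group cannot be reproduced, because no rates, effect size or power are given.

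**Inputs.** From the protocol: 40 per group (III(x)), chi-squared test and significance level 0.05 (VI). Assumed: a two-sided test, no continuity correction, no procedure effect, and two sites of 40 patients each. Site A supplies a share s of the SB group and 1 − s of the PPV+SB group; site B supplies the mirror image. Print rates are rA at site A and rB at site B, whichever procedure is done. The documents give no rates by site, so every pair of rates below is an assumption.

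**Spurious difference.** The expected difference between groups is (2s − 1) × (rB − rA). For 35.2% and 60%, the gap is 24.8 points:
- s = 0.65: 0.30 × 24.8 = 7.4 points
- s = 0.75: 0.50 × 24.8 = 12.4 points
- s = 0.90: 0.80 × 24.8 = 19.8 points

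**False-positive rate.** The SB print count x is the sum of Binomial(40s, rA) and Binomial(40(1 − s), rB); the PPV+SB count y is the mirror image. With m = (x + y)/80, the test rejects when ((x − y)/40)² / [m(1 − m) × 2/40] exceeds 3.841. Summing the exact probabilities over all x and y gives:

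| Assumed site rates | 50/50 | 60/40 | 65/35 | 75/25 | 90/10 |
|---|---|---|---|---|---|
| 35% and 45% | – | – | 6.0% | 7.6% | – |
| 35% and 50% | 5.1% | 6.0% | 7.1% | 10.8% | 20.0% |
| 35.2% and 60% | 4.9% | 7.3% | 10.4% | 20.8% | 45.1% |

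(A dash marks a combination not reported here.) At a balanced mix the test holds its level, so the excess comes from the imbalance between sites and not from the site difference alone.

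**Does stratifying by site repair it?** In 200,000 simulated trials per mix at 35.2% and 60%, a Mantel-Haenszel test stratified by site rejected in about 5% at 65/35, 75/25 and 90/10.

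**What stratifying costs.** The information from a site with n1 SB and n2 PPV+SB patients is n1·n2/(n1 + n2). Twice the sum over the two sites gives the effective size per group:
- 60/40: 24 × 16/40 = 9.6 per site; 2 × 19.2 = 38.4
- 75/25: 30 × 10/40 = 7.5 per site; 2 × 15 = 30
- 90/10: 36 × 4/40 = 3.6 per site; 2 × 7.2 = 14.4
- 100/0: 0, so the procedure effect cannot be separated from site

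**The case against.** **The imbalance is not shown.** Section I includes these practices for "as the site to study retinal displacement following RD repair using either SB or PPV with SB" and cites their higher volume of those methods. Section V expects consenting staff to be familiar with both operations. Both passages suggest sites that do both procedures. This stands: a reader might infer that the sites will divide by procedure, and the protocol does not support that. It shows only that nothing prevents it.

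**The assumed rates are not site rates.** Section I quotes 35.2% after PPV in one study, and 71.4% with gas against 22.2% with silicone oil in another. A reader might take that spread as evidence of how far two sites could differ. It is not: the figures come from different vitrectomy studies and tamponades. The 45% figure needs both a 90/10 mix and a gap of about 25 points. Milder assumptions give 6% to 8%.

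**The analysis plan may deal with it.** Stratification is often left to the statistical analysis plan, which is not at hand, and section VI promises coefficients with confidence intervals, which may hint at a model. This stands in part. The point is therefore not that a site adjustment is missing everywhere, but that the test the protocol does state can be improved at little cost.

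**A compulsory minimum of each procedure per site is a trade-off.** It might mean turning away eligible patients in a cohort where III(viii) offers the study to all who qualify. It is not a clear improvement and is not recommended here. FAF settings are a separate measurement question.

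**A larger bias remains.** Section I says the combined operation is commonly used for larger or more complex detachments. That confounding by indication exists within each site, and stratifying by site leaves it in place. This stands.

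**Conclusion.** The point holds as a conditional one. Under the plan as written, a difference between sites in print detection biases the procedure comparison whenever the procedure mix differs by site, and the stated test has no protection against this. The size cannot be known from the protocol. Under the assumed rates and mirror-image mixes, the false-positive rate runs from about 6% (35% and 45%, 65/35 mix) to about 45% (35.2% and 60%, 90/10 mix), against a nominal 5%. The corresponding spurious differences are 0.30 × 10 = 3 points and about 20 points.

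This is a worthwhile, inexpensive improvement to the analysis. It is not evidence that the comparison will be confounded with site.

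**What to change.** In section VI, make the primary comparison a site-stratified one: a Cochran-Mantel-Haenszel test, or logistic regression with site as a term. Add site to the data items under III(ix) so that it is in the analysis dataset, and report the print-by-procedure table separately for each site. During recruitment, monitor the procedure mix by site, so that a near-complete split is noticed while it can still be considered.

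The wording change and the extra data item cost almost nothing, but the stratified analysis is not free. Effective size per group falls from 40 to about 38 at a 60/40 mix, 30 at 75/25 and 14 at 90/10. If each site supplies only one procedure, no analysis can recover the procedure effect. The report should also state that stratifying by site does not address the surgeon's selection of patients for each operation within a site.

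### The plan points to a completers analysis in which the 3-month readings play no part for the 20% expected to be lost over the 12-month visit

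*Protocol*

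**What the plan says.** Protocol section V (Consent) gives the size of the expected loss and its cause: "Given that 12-month followup can be problematic for patients who live a great distance from the study sites, a 20% dropout rate is anticipated".

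Section III(x) (Sample size) sets two groups of 40: "A total sample size of 40 subjects with macula-off detachments undergoing scleral buckles will be recruited", and "A second group of 40 subjects with macula-off retinal detachments undergoing combined vitrectomy and scleral buckle placement will also be recruited". It then states: "Anticipating a dropout rate of 20%, we calculated a total of 100 patients in the entire study". Section III(viii) (Recruitment plan) says that recruitment runs until the required number have both enrolled and finished the study, with 12 months of follow-up each.

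Section III(v) (Interventions) says that the study assessments are "performed at the 3 and 12 month postoperative visit". They cover fundus autofluorescence (FAF), OCT and "sensory testing with the M chart and the Aniseikonia test, as detailed below".

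Section III(vii) (Outcome measures) makes the primary outcome the presence of vessel prints on FAF and gives it no time point. The hypothesis in III(i) refers only to the first 12 months.

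Section VI (Data Analysis) names an unpaired t-test or a non-parametric test for continuous data and a chi-squared test for categorical data. It then says: "Per protocol analysis will be used". The term is not defined.

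**The concern.** The expected loss is put down to one late visit, and the primary outcome is also measured at an earlier one. A participant who attends at 3 months and then stops coming has a primary-outcome reading, an M chart score and an aniseikonia result. Nothing in the protocol says what becomes of them. The sizing, the recruitment target of participants who finish, the per-protocol rule and the single-time tests all lean towards leaving that participant out.

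Two things are at stake. One is precision, since readings already taken would not be used. The other, probably more important, is selection. The surgeon chooses the procedure, and the Background says that the combined operation is common for larger or more complex detachments. Willingness to return at a year could therefore differ between the two groups, and it may be related to how well the eye sees. An analysis limited to those who return would add this selection to the confounding that the design already carries.

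**Working it through.** **Inputs from the protocol.** 40 per group and a total of 100 (III(x)); 20% dropout (III(x) and V); assessments at 3 and 12 months (III(v)); significance level 0.05 (VI), taken as two-sided; 35.2% displacement after vitrectomy (Background). The last figure belongs to neither study group and serves only as an illustration.

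**Inputs assumed, because the protocol does not give them.** The share *s* of the 20 expected dropouts who have a 3-month reading; the correlation ρ between the 3- and 12-month results; power of 80% at 40 per group; a comparator displacement rate of 10%.

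**Step 1: reproduce the plan's figure.** 80/(1 − 0.20) = 100, or 50 per group, which matches exactly. The alternative 80 × 1.20 = 96 does not. The 20 extra participants are therefore sized as contributing nothing.

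**Step 2: upper bound, with a 3-month reading counted in full.** Analysable N = 80 + 20s. Interval width relative to 80 is √(80/N). Power is Φ(2.802·√(N/80) − 1.960).

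| s | N | Relative width | Power |
|---|---|---|---|
| 0 | 80 | 1.000 | 80% |
| 0.25 | 85 | 0.970 | 82% |
| 0.50 | 90 | 0.943 | 84% |
| 0.75 | 95 | 0.918 | 86% |
| 1.00 | 100 | 0.894 | 88% |

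**Step 3: 12 months as the target.** The 3-month result then only informs the missing one. As a rough approximation, effective N = 80 + 20·s·ρ². With s = 0.75:

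| ρ | Effective N | Relative width | Power |
|---|---|---|---|
| 0.5 | 83.75 | 0.977 | 82% |
| 0.7 | 87.35 | 0.957 | 83% |
| 0.9 | 92.15 | 0.932 | 85% |

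**Step 4: the same on the outcome scale.** For 35.2% against an assumed 10%, the standard error of the difference is √[(0.352 × 0.648 + 0.10 × 0.90)/n] = √(0.3181/n). This gives 8.9 percentage points at n = 40 per group, 8.4 at 45 and 8.0 at 50.

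**Step 5: selection, illustration only.** If 20% of one group is lost and their displacement rate differs by an assumed 20 points from that of those who stay, the observed rate in that group differs from its full-group rate by 0.20 × 0.20 = 4 points. The error in the comparison is smaller if the other group loses similar patients, and cancels if the losses are alike.

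**The case against.** The strongest reply is that the protocol nowhere states a 12-month completers analysis. The primary outcome has no time point and per protocol is undefined. A chi-squared test on 3-month FAF would fit section VI as written and would include everyone seen at 3 months. That stands: the completers reading is an inference. But if the text allows either analysis, the primary time point needs fixing all the same.

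A second reply is that models for partial follow-up belong in a statistical analysis plan, which may exist but is not shown. This stands in part. However, the protocol itself fixes the tests, the per-protocol rule and the visit schedule, so the point concerns what it chose and not detail that it left out.

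Third, section III(iii) already excludes patients unable to attend follow-up to 12 months. This limits the selection by distance, but the protocol expects 20% dropout in spite of it.

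A reader might also infer three stronger things that the documents do not support:

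- **That the sample size is wrong.** It is not. Dividing by one minus the dropout rate is standard and protects the 40 per group.
- **That many of the dropouts could be kept.** The protocol gives no 3-month attendance.
- **That those who stop after 3 months never complete the metamorphopsia questionnaire.** Section III(v) does not list it among its assessments, but the list is introduced as an inclusion and not as exhaustive. Section III(vii) gives the questionnaire no time point. The Appendix 1 flowchart is readable only as fragments, and it shows FAF and the M chart under 12 months too, although III(v) also places them at 3 months.

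**Conclusion.** The point holds as a better use of data already planned, not as an error of calculation. As written, the plan leans towards an analysis in which the 3-month FAF, M chart and aniseikonia readings do nothing for participants who miss month 12, in a surgeon-selected comparison where return may differ between groups.

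The gain in precision is modest. The ceiling of about 11% narrower intervals requires every dropout to have a 3-month reading that is interchangeable with a 12-month one, and no text supports that. With 12 months as the target, 75% of dropouts seen at 3 months and a correlation of 0.5 to 0.9, effective N is about 84 to 92 in place of 80, and intervals are about 2% to 7% narrower. Attendance and correlation are both assumed.

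Reducing selection may be the larger benefit, but the documents do not allow it to be sized. The 4-point figure is an illustration and should not be read as an estimate of bias in this study.

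**What to change.** 1. Name the primary time point in III(vii), for example the SB versus PPV+SB contrast at 12 months.
2. In section VI, replace the per-protocol rule for the primary comparison with inclusion of every participant who has at least one post-operative FAF image.
3. Analyse the yes/no outcome with a likelihood-based mixed logistic model with procedure, visit and their interaction, and take the contrast at the named time point. Multiple imputation of the 12-month result using the 3-month result is an alternative. Unweighted GEE is less suitable, because it generally needs data missing completely at random and so would not reliably remove the selection at issue.
4. Use a mixed model in the same way for M chart and aniseikonia.
5. Report 12-month completers only as a sensitivity analysis.
6. Reconcile Appendix 1 with III(v) on the 3-month visit. Optionally, give the metamorphopsia questionnaire at 3 months if it is not already given then.
7. Keep enrolment at 100. With 3-month attendance unknown, there is no basis for reducing it.

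The cost is a change of analysis wording and, at most, one questionnaire at a visit already scheduled. The price in assumptions is that 12-month results must be missing at random given the 3-month findings. Participants seen at neither visit are not recovered.
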